3.4. ALLOGENEIC, HUMAN CORD TISSUE-DERIVED MSC - Duke

The Marcus Center for Cellular Cures at Duke University, is manufacturing third party, allogeneic, human cord tissue-derived MSCs (hCT-MSC) in the Robertson GMP Cell Manufacturing Laboratory which are being utilized in clinical trials to treat pediatric patients with autism spectrum disorder (IND 17313), cerebral palsy (IND 17921), hypoxic ischemic encephalopathy (IND 17313) and adults with osteoarthritis of the knee (IND18414). Manufacturing is identical for all products used in these clinical trials. The final product is a cryopreserved P2 product that is thawed and diluted on the day of infusion.

The MSCs are manufactured from cord tissue donated to the Carolinas Cord Blood Bank at Duke, a FDA licensed public cord blood bank (DUCORD), by mothers delivering healthy term male babies by Cesarean section, after full written informed consent from the newborn infant's mother. Full donor screening and testing is performed in accordance with regulatory requirements. The cord tissue is harvested in the operating room and placed in a sterile container containing 200mL of sterile Plasmalyte-A solution without antibiotics. The tissue is transported in a validated container at room temperature by a dedicated and trained courier to the manufacturing lab on the same day of the baby's delivery. In the GMP lab, in the clean room, it is cut into 2" sections and digested with 4 GMP grade enzymes (DNAase, collagenase, alpha hyaluronidase, and papain) on the Miltenyi Octo tissue dissociator. The resultant cell suspension is plated in a cell stack with SXFM media (Irving Scientific) supplemented with human platelet lysate in a 5-layer cell stack flask (Corning) and cultured for 7-10 days. When confluent, the cells are harvested (PO) and replated in hyperstacks (Corning) for 7-8 days to confluence and harvested (P1) and then replated again and cultured to P2. The P2 harvest is washed and cryopreserved in a final concentration of 10% DMSO in dextran in 5 finger cryobags (Pall Medical), frozen in a controlled rate freezer and stored in the vapor phase of liquid nitrogen until use. A portion of the PO and P1 cells are also cryopreserved and stored as part of a master (PO) and working (P1) cell bank during manufacturing.

A representative P2 dose is thawed and tested for characterization (phenotype and differentiation),

Confidential Page 12 of 32

sterility (bacT-alert and adventitial virus testing), endotoxin, mycoplasma, P53 mutation, and functional assays (suppression of third party T-cell proliferation and suppression of microglial activation). All assays must pass specifications for release. Stability for the post thaw product is 4 hours at room temperature.

On the day of infusion, the product is thawed, diluted 1:1 with Plasmalyte-A with 5% Human Serum Albumin (HSA), and assessed for total nucleated cell count and viability on a Cellometer. The volume needed for the patient's dose is then calculated, removed and diluted in additional Plasmalyte-A with 5% HSA to 20-40mL and taken to the bedside for infusion. The release specification for viability post thaw is \geq 70%.

3.5. ALLOGENEIC, HUMAN CORD TISSUE DERIVED MSC – University of Miami

Clinical Research Cell Manufacturing Program (CRCMP) at the University of Miami has manufactured allogeneic hCT-MSCs from sourced cord tissue obtained from Carolinas Cord Blood Bank (CCBB) at Duke. Screening of allogeneic donors will follow standard transplant practices and all allogeneic donors will meet allogeneic donor eligibility criteria as outlined in 21 CFR Part 1271 including FDA screening guidance on Zika and SAR CoV-2 The allogeneic hCT-MSCs will be derived from normal donors meeting criteria for allogeneic unrelated human cord tissue.

Cell manufacturing is done at the Clinical Research Cell Manufacturing Program (CRCMP) laboratory, Interdisciplinary Stem Cell Institute (ISCI), Miller School of Medicine, University of Miami. Cells are manufactured in compliance with current Good Manufacturing Practice (cGMP) and current Good Tissue Practice (cGTP) regulations. CRCMP is accredited by Foundation for Accreditation of Cellular Therapy (FACT) and American Association of Blood Bank (AABB). In brief, umbilical cord tissue will undergo the process to obtain MSCs. Cells obtained in initial passages are cultured and expanded in three passages. The expansion is performed in tissue culture flasks incubated in 37°C, 5% CO₂ humidified incubators. At the final passage, MSCs are counted and cells viability are determined. Samples are collected for cell phenotypes assay, mycoplasma PCR testing, sterility testing, adventitial virus testing, and endotoxin assay. After harvest, cells are aliquoted into cryopreservation bags containing 120 to 130 million cells and cryopreserved using a control rate freezer. The bags are stored in the vapor phase liquid nitrogen storage cryogenic freezers at ≤ -120 °C.

The cryogenic freezer is located in the secured storage area accessible only by authorized personnel. Laboratory Director and Quality Assurance Manager will review the production records and quality control testing results to release the product for clinical use.

For cell manufacturing of hCT-MSC, cross-references to CMC sections of University of Miami is provided with this application. Please refer to cross reference letter to BB IND #17324 of University of Miami.

3.6. CLINICAL EXPERIENCE WITH HCT-MSC

The current hCT-MSC product manufactured at Duke has been used in >90 children given >160 doses of 12-6 million hCT-MSC/kg intravenously, in approximately 54 adults with OA of the knee at 10-20M cells/dose given directly into the knee joint, and in 1 adult with bronchiectasis under an IND at a dose of 100 million total cells. In the proposed Phase 1 pilot portion of this study, we capped the dose per infusion at 100 million cells (total absolute dose) to follow conventions in an ongoing trial where absolute doses of 200 million cells appeared less effective than 100 million cells.

Confidential Page 13 of 32

The first 10 patients enrolled in this study were enrolled on the Phase 1, open label portion of this study. That cohort was fully enrolled with 8 patients treated at DUMC and 2 patients treated at the Boca Raton Regional Hospital. The median age of the patients was 61.5 years (29-79 years), 70% were female, 60% were Caucasian, and 30% were Hispanic. There were 4 SAEs reported in the trial, all resulting in death occurring on days 7, 27, 39, and 344 on study. None were deemed related to the MSC product. The MSC product infusions were well tolerated. There were no infusion related AEs or SAEs.

3.6.1 SAFETY

All patients will be pre-medicated before each dose of hCT-MSCs with a parenteral dose of diphenhydramine (12.5-25mg) and hydrocortisone 0.5 mg/kg IV approximately 30-60 minutes prior to infusion. Using this approach, infusion- associated reactions are uncommon (<1%) and mild. Observed reactions consist of, rash, bronchospasm and rarely, transient hypotension. If an adverse event occurs after the first or second dose, the subsequent doses will not be administered.

The following adverse events, deemed *not related* to the MSC product have been reported in patients receiving BM-MSCs for treatment of graft versus host disease following a blood or marrow transplant where more than 1,000 adults have been treated: increased blood pressure, low blood pressure, difficulty breathing, pain in the abdomen or stomach, abdominal distension, bleeding in the gastrointestinal tract, swelling in legs or arms, nausea, vomiting, diarrhea, dizziness, itching, rash, fever, elevation of blood cells (eosinophils), increase in blood levels of various laboratory values (including alkaline phosphatase, creatinine, lactate dehydrogenase, alanine transaminase and glucose), hypocalcemia, ascites, kidney impairment, hepatomegaly, neutropenia, thrombocytopenia graft versus host disease, chest discomfort, chest pain, oral yeast infection, muscle weakness, joint pain, back pain, cold sweat, headache, and depression.

Other theoretical risks include engraftment and differentiation of transplanted MSCs with ectopic tissue formation. In addition, MSCs in the paracrine and endocrine systems may promote tumor growth and metastasis by diminishing or suppressing the antitumor immunity and inducing neovascularization.

Long term safety information of the use of MSCs is still unknown, but 10 year follow-up in hundreds of treated patients has not revealed any serious problems to date.

Risks associated with the use of diphenhydramine include dizziness, sedation, dry mucous membranes, dryness of the nose and throat, and thick sputum. Allergic reaction can occur, which would, include swelling of the throat and trouble breathing.

Possible side effects of corticosteroids include fluid retention and weight gain, muscle weakness, peptic ulcer; high blood pressure; permanent changes in the bones; increase in infection risk and hyperglycemia.

Confidential Page **14** of **32**

3.7 TREATMENT PROTOCOL PROCEDURES RATIONALE

3.7.1 CLINICAL DOSE SELECTION

The dose for the first 10 patients will be 1 million cells/Kg (with a maximum dose of 100 million cells) with 70% viability post thaw. The dose for the subsequent randomized patients will be 100 million cells (absolute fixed dose) daily x 3 days without adjustment for weight. Analysis of total nucleated cell count and nucleated cell viability is determined in an automated device called a Cellometer (Nexcelom). This dose has been derived from previous clinical studies where hCT-MSCs have been infused at a dose of 2-6 million cells/Kg.

3.7.2 CELL SHIPMENT, PREPARATION FOR ADMINISTRATION AND INFUSION - Duke

The hCT-MSC cells manufactured at Duke will be shipped prior to initiation of treatment from the Robertson GMP Cell Manufacturing Laboratory at Duke University to the outside treatment site(s) in a dry shipper validated to maintain temperatures <-150 degrees C for 8 days. The cells can be maintained in the dry shipper or transferred to a vapor phase liquid nitrogen freezer which is continuously monitored for temperature. On the day of infusion, the cells will be thawed in a cell therapy laboratory or in a room near the bedside at the infusion site, per standard operating procedure, and aspirated into a sterile syringe containing an equal volume of PlasmaLyte-A with 5% HSA. A TNCC and viability will be performed and cell dose adjusted to 1 million cells/kg with a viability of ≥70% (maximum dose 100 million cells). After this initial dilution, the volume containing the dose for the patient will be further diluted into additional PlasmaLyte-A + 5% HSA to a total volume of 80mL placed into a transfer bag, and transported to the bedside. There they will be administered over approximately 30-60 minutes by gravity. Three daily infusions, 12-36 hours apart will be administered as long as the patient does not have a reaction or other adverse event after the first or second infusion. If an infusion reaction or adverse event related to the hCT-MSC infusion occurs, subsequent infusions will not be administered. For the first 3 consecutive patients on the phase 1 portion of the study there will be a 3 day staggering interval between consecutive patients before the next patient is treated. After the first 3 patients have no detected acute and/or subacute adverse events, the study will continue with open enrollment to complete 10 consecutive patients in phase 1. For phase 2, patients will be randomized 2:1:1 against placebo with patients randomizing to MSCs will be further randomized to receive either Duke of Miami cells.

After release, the labeled product will be delivered and issued to the appropriate medical staff in a validated temperature monitored cooler. Clinical coordinator or medical staff maintains custody of the product container to ensure that the product is kept in the proper temperature until it is ready to be removed for infusion.

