2. PROTOCOL SYNOPSIS

This is a 50 patient, Phase 1/2a multi-center pilot study to test the safety and to describe the preliminary efficacy of intravenous administration of allogenic human cord tissue mesenchymal stromal cells (hCT- MSC) as an investigational agent, under U.S. INDs 19968 (Duke) and 19937 (U Miami) to patients with acute respiratory distress syndrome (ARDS) due to COVID-19 infection (COVID-ARDS). Patients will be eligible for treatment with 3 daily consecutive doses of hCT-MSC at 1 million cells/kg (max dose 100 million cells) in the phase 1 portion of the study or a fixed dose of 100 million cells daily x 3 days, 12-36 hours apart in the phase 2 portion of the study, if they have a

Confidential Page 8 of 32

confirmed diagnosis of COVID-19 and meet clinical and radiographic criteria for ARDS. The primary endpoint is short-term safety of hCT-MSC infusions given on this schedule. The key secondary endpoints are 28 day survival, an increase in PaO2/FiO2 ratio by 50% at 96 hours, days to hospital discharge to home or rehab, and number of days requiring mechanical or non-invasive ventilation or high flow nasal cannula.

The study will be executed in two phases. The first 10 consecutive patients will all receive investigational product. The second part of the study is a randomized, controlled trial in 40 additional patients. The overall aim of the study is to establish safety and to gain critical information as to whether patients with COVID-ARDS will benefit from MSC infusions. Results from the first 10 patients will be compared with concurrent outcomes utilizing standard of care treatments in participating hospitals and in published reports in the medical literature. Results from the additional 40 patients will be analyzed as a randomized placebo control trial. The trial is relying on focused eligibility of the participants (patients with ARDS), single cohort with short trial time (4 weeks), and simple assessment of clinical outcome (survival, improvement of ARDS). This is a sequential design in the sense that after the first 10 patients are evaluated a decision will be made by the PIs and the Data Safety Monitoring Board whether to proceed with the exploratory randomized portion of the study.

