In this study, we will test the safety and describe the efficacy of human cord tissue derived MSCs (hCT-MSC) in patients with COVID-ARDS. It is hypothesized that COVID-ARDS occurs as a consequence of a cytokine storm (or cytokine release syndrome, CRS) and occurs in ~3-5% of COVID-19 infected patients. Involved cytokines include IL-6, IL-8, IL-10, THP-1M, TNF-alpha, and others. hCT-MSCs have been shown to suppress RNA expression and secretion of these cytokines by macrophages and T-cells in vitro. They also have a higher proliferative capacity than MSCs derived from adult derived bone marrow or adipose tissue. 41 hCT-MSCs, manufactured at Duke in the Robertson GMP Cell Manufacturing Laboratory in the Marcus Center for Cellular Cures, have been tested in 115patients in clinical trials under INDs 17313, 17921 and 18414 over the past 4 years.⁴² Safety profiles have been extremely favorable. We now propose to utilize these cells in a sequential study where part I is a Phase 1 safety study in 10 consecutive adult patients with COVID-ARDS dosing at 1 million cells/kg (max dose 100M cells) given intravenously, daily x 3. The primary endpoint of this study is safety. Key secondary endpoints are 28 days survival, an increase in PaO2/FiO2 ratio by 50% at 96 hours, days to hospital discharge to home, and number of days requiring mechanical ventilation. If safety is demonstrated in this 10 patient cohort, a second phase of this trial will describe the efficacy of hCT-MSCs in an additional cohort of 40 patients who will be randomized in a blinded fashion 2:1:1 to placebo, hCT-MSC manufactured at Duke, or hCT-MSC manufactured at Miami. This randomization plan will yield 20 participants on placebo and 10 in each of the hCT-MSC arms. The two hCT-MSC arms will be pooled for analyses comparing treated patients to placebo.

Phase I, Safety

10 patients
1x10^6/kg patient weight
(max 100x10^6)

Phase II Randomization, Efficacy

Placebo

hCT-MSCs

10 patients
DUKE
Fixed dose 100x10^6

10 patients
UNIVERSITY OF MIAMI
Fixed dose 100x10^6

Confidential Page 11 of 32

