3.7.2.1 CELL SHIPMENT, PREPARATION FOR ADMINISTRATION – University of Miami

The hCT-MSC cells manufactured at the University of Miami will be shipped prior to initiation of treatment from CRCMPlab at the University of Miami. Upon receiving request for product, a product(s) bag with the appropriate dose is assigned. The preparation of the final product for administration will follow the Standard Operating Procedures maintaining under standardization of procedures. The principal investigator at clinical site will submit a signed request for the final product with date and time of product infusion to processing laboratory prior to the scheduled date. On the day of product infusion, the appropriate number of released frozen bags will be thawed in a 37±1°C water bath. In a biological safety cabinet, the cell suspension is transferred to conical tubes and slowly diluted with buffer containing

Confidential Page **15** of **32**

PlasmaLyte A supplemented with 1% human serum albumin (HSA). The diluted suspension will be centrifuged and the cell pellet will be suspended in the dilution buffer. Viability and cell count will be measure on a cellometer (Nexcellom). The cells will be centrifuged and the cell pellet resuspended in the buffer to a required dose in a total volume of 80mL. Cell dose will be loaded into an infusion bag. The prepared product will undergo a final inspection and release process.

After release, the labeled product will be delivered and issued to the appropriate medical staff in a validated temperature monitored cooler. Clinical coordinator or medical staff maintains custody of the product container to ensure that the product is kept in the proper temperature until it is ready to be removed for infusion.

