5.2. DOSE

The hCT-MSC infusion, 1 million cells/kg (maximum 100 million cells) with >70% viability (based on Cellometer), is infused over approximately 30-60 minutes for the first 10 patients. Subsequent patients, randomizing to treatment, will receive 100 million cells/dose per infusion without an adjustment for weight. A second and third infusion of the same number of cells will be given 24 hours (+/- 6 hours) and 48 hours (+/- 6 hours) later, respectively.

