9.2 RANDOMIZATION PLAN

In Phase II of this study, a total of 40 participants will be randomized in a ratio of 2:1:1 to placebo, hCT-MSC manufactured at Duke, or hCT-MSC manufactured at Miami. This randomization plan will yield 20 participants on placebo and 10 in each of the hCT-MSC arms. The two hCT-MSC arms will be pooled for analyses comparing treated patients to placebo (see below). The infusion will be blinded so that the medical teams and the patients/LARs will not know which product (placebo, Duke MSC or Miami MSC) the patient receives. There will be unblinded technicians in the laboratories preparing the cells and placebo for infusion, but the final product configuration will be the same for all infusions.

Phase I, Safety 10 patients 1x10^6/kg patient weight (max 100x10^6) Phase II Randomization, Efficacy Placebo hCT-MSCs 10 patients DUKE Fixed dose 100x10^6 10 patients UNIVERSITY OF MIAMI Fixed dose 100x10^6

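### Section 3.7.2 still tells the laboratory to prepare Duke cells at 1 million cells/kg with no phase limit, against a fixed Phase II dose of 100 million cells

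*Combined protocol and SAP*

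**What the plan says.** The Phase II dose is stated consistently in five places:

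- The synopsis (section 2) gives "a fixed dose of 100 million cells daily x 3 days, 12-36 hours apart in the phase 2 portion of the study".
- The schema in section 3.2 labels the cell arms "Fixed dose 100x10^6".
- Section 3.7.1 says: "The dose for the subsequent randomized patients will be 100 million cells (absolute fixed dose) daily x 3 days without adjustment for weight".
- Section 5.2 says that patients randomized to cells "will receive 100 million cells/dose per infusion without an adjustment for weight".
- The schema in section 9.2 reads "10 patients DUKE Fixed dose 100x10^6" and gives the same dose for Miami.

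Sections 3.7.1 and 5.2 confine the weight-based dose (1 million cells/kg, capped at 100 million) to the first 10 patients.

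Section 3.7.2 describes how the Duke product is thawed, counted and made up. There the instruction is "cell dose adjusted to 1 million cells/kg with a viability of ≥70% (maximum dose 100 million cells"), with no mention of phase. Later in the same paragraph the text turns to the randomized part: "For phase 2, patients will be randomized 2:1:1 against placebo". The matching Miami section, 3.7.2.1, contains no per-kg rule. Those cells are resuspended "to a required dose in a total volume of 80mL".

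**The concern.** For a Phase II patient assigned to Duke cells and weighing less than 100 kg, section 3.7.2 and section 5.2 cannot both be followed. The paragraph in 3.7.2 names the phase where it means to, for the staggering of the first three patients and for the randomization. The dose sentence carries no such marker, so its position does not make it Phase I text. Section 3.6 reports that the Phase I cohort is fully enrolled, so every Duke dose still to be prepared is for a Phase II patient, for whom the per-kg target is wrong.

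At stake is the dose delivered in one of the two cell arms. If the Duke arm were dosed by weight and the Miami arm at 100 million, the pooled cell group would be a mixture of doses. The separate Duke comparison with placebo in section 9.4 would also concern a lower dose than the protocol states. The two cell arms would then differ in dose as well as in manufacturer.

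**Working it through.** The plan gives no figure of its own to reproduce here. The check compares the dose statements and then works out what the 3.7.2 sentence would deliver.

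**Inputs**

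- Duke preparation rule: 1 million cells/kg, maximum 100 million (section 3.7.2).
- Phase II dose: 100 million cells per infusion, fixed (synopsis, 3.2, 3.7.1, 5.2, 9.2).
- Number of infusions: 3 (synopsis, 3.7.1).
- Phase II cell arms: 10 Duke and 10 Miami, pooled against 20 on placebo (9.2).
- Body weight: not given in the documents. Weights of 50 to 100 kg are assumed.

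**Formulas** (doses in millions of cells, w = weight in kg)

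- Dose per infusion under 3.7.2 = min(w, 100).
- Total over three infusions = 3 × min(w, 100), against 3 × 100 = 300 planned.
- Shortfall = 100% − min(w, 100)%.
- Pooled mean per infusion = (10 × Duke mean dose + 10 × 100) / 20.

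**Results**

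| Weight (kg) | Duke dose per infusion | Total of three | Shortfall | Pooled mean per infusion if this is the Duke mean |
|---|---|---|---|---|
| 50 | 50 | 150 | 50% | 75 |
| 60 | 60 | 180 | 40% | 80 |
| 70 | 70 | 210 | 30% | 85 |
| 80 | 80 | 240 | 20% | 90 |
| 90 | 90 | 270 | 10% | 95 |
| 100 or more | 100 | 300 | 0% | 100 |

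For example, with a Duke mean of 70 kg and nobody above 100 kg, the pooled mean is (10 × 70 + 10 × 100) / 20 = 1,700 / 20 = 85 million. The condition that nobody exceeds 100 kg matters because of the cap: at the same mean weight, any patient above 100 kg would pull the mean dose below the mean weight.

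**Does nearby text correct the sentence?** Section 5.2.1, the administration checklist, gives only a maximum of 100 million cells, which a 70 million dose also satisfies. Section 3.7.2.1 refers to the required dose without a number. Section 3.7.2 is therefore the only one of the two cell-preparation sections that states a numeric dose, and that number is the Phase I one.

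**The case against.** The strongest reply is that the dose is already settled. Section 5.2 is the dose section of the treatment plan, section 3.7.1 comes directly before the disputed text, and three other places agree. Section 3.7.2 sits in the background and rationale chapter and deals with shipment and handling. Under-dosing would need staff to follow one sentence over five explicit statements. The section also refers to a standard operating procedure, which may already be right. This stands as far as intent goes: there is no real doubt about which dose is meant. It does not make the sentence correct, because it is still a numeric preparation instruction with no valid use left.

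Second, the size of the shortfall rests on assumed weights and on all Duke patients being dosed by weight. That is true, and the figures should be read as conditional. The documents also give no dose-response information below 100 million cells, so no effect on outcomes can be derived.

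Third, section 9.4 plans no direct Duke-versus-Miami comparison, and section 9.1.2 describes the Phase II analysis as descriptive. Randomization also keeps each comparison with placebo valid for the dose actually given. All of this stands. A difference in dose between the cell arms would matter for describing the pooled and Duke-specific results, and for anyone setting the two arm-specific results side by side. It would not bias a planned test between the arms.

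Fourth, nothing in the Miami section is wrong. That is also correct, and adding a number there is alignment only.

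**Conclusion.** The concern holds. Section 3.7.2 contradicts the fixed Phase II dose stated in the synopsis and in sections 3.2, 3.7.1, 5.2 and 9.2. It is leftover Phase I wording in an operational paragraph, not an open question about the intended dose.

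If the sentence were followed, only Duke-arm patients under 100 kg would be affected. On the assumed weights the loss runs from 10% of the dose at 90 kg to 50% at 50 kg, and the pooled cell group would average 75 to 95 million cells per infusion for Duke means of 50 to 90 kg with nobody above 100 kg. The documents do not show whether preparation has in fact followed this sentence. The correction should be made, but the design and the planned comparisons do not depend on it.

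**What to change.** In section 3.7.2, limit the adjustment to 1 million cells/kg (maximum 100 million) to Phase I, and add that Phase II patients receive a fixed 100 million cells per infusion whatever their weight. Put the same fixed number in section 3.7.2.1 so that the two preparation sections match. The maximum-only wording in section 5.2.1 could be aligned in the same edit. Check that the Duke preparation procedure states the fixed Phase II dose.

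The cost is one sentence in 3.7.2, one number in 3.7.2.1 and one document check. With the change, every Phase II Duke patient who completes treatment is due 100 million cells per infusion and 300 million in total. No sample size, power or analysis statement changes.
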